4.3 TREATMENT COMPLIANCE

Patients are requested to bring all remaining trial medication including empty package material with them when attending visits.

The Investigator or his/her designate will count the number of the returned tablets and calculate the compliance based on the number of tablets taken, divided by the number of tablets that should have been taken since last visit, multiplied by 100. See formula below.

$$\text{Compliance (\%)} = \frac{\text{Number of tablets actually taken since last tablet count} \times 100}{\text{Number of tablets which should have been taken in the same period}}$$

Compliance should be between 80% and 120%. Compliance should be emphasised with a goal of at least 80% compliance rate. However, randomised patients will not be discontinued for poor compliance without prior discussion with the monitor or designee.

Patients who are not compliant with their medication should again be carefully interviewed and again re-informed about the purpose and the conduct of the trial.

5 VARIABLES AND THEIR ASSESSMENT

5.1 TRIAL EFFICACY ENDPOINTS

5.1.1 Primary endpoint(s)

The composite primary endpoint for this trial is the time to first event of adjudicated CV death or adjudicated HHF in patients with Heart Failure with preserved Ejection Fraction (HFpEF).

5.1.2 Secondary endpoint(s)

The key secondary endpoints which are part of the testing strategy, are the following:

1. Occurrence of adjudicated HHF (first and recurrent),
2. eGFR (CKD-EPI)_{cr} slope of change from baseline

Other secondary endpoints (not part of confirmatory testing hierarchy on trial level) are the following:

- Time to first occurrence of chronic dialysis or renal transplant or sustained* reduction of $\geq 40\%$ eGFR (CKD-EPI)_{cr} or
 - sustained eGFR (CKD-EPI)_{cr} < 15 mL/min/1.73 m² for patients with baseline eGFR ≥ 30 mL/min/1.73 m²
 - sustained eGFR (CKD-EPI)_{cr} < 10 mL/min/1.73 m² for patients with baseline eGFR < 30 mL/min/1.73 m²

*An eGFR (CDK-EPI)_{cr} reduction is considered sustained, if it is determined by two or more consecutive post-baseline central laboratory measurements separated by at least 30 days (first to last of the consecutive eGFR values).

Chronic dialysis is defined as dialysis with a frequency of twice per week or more often for at least 90 days.

- Time to first adjudicated HHF
- Time to adjudicated CV death
- Time to all-cause mortality
- Time to onset of DM (defined as HbA1c $\geq 6.5\%$ or as diagnosed by the Investigator) in patients with pre-DM defined as no history of DM and no HbA1c ≥ 6.5 before treatment, and a pre-treatment HbA1c value of ≥ 5.7 and < 6.5
- Change from baseline in clinical summary score (HF symptoms and physical limitations domains) of the Kansas City Cardiomyopathy Questionnaire (KCCQ) at week 52
- Occurrence of all-cause hospitalisation (first and recurrent)

5.1.3 Further endpoints

- Time from first to second adjudicated HHF

Proprietary confidential information © 2019 Boehringer Ingelheim International GmbH or one or more of its affiliated companies

- Time to first all-cause hospitalisation
- Occurrence of adjudicated HHF within 30 days after first adjudicated HHF
- Occurrence of adjudicated HHF and CV death. This endpoint will account for clinical hierarchies in composite outcomes, i.e. CV death is ascribed greater importance than HHF (see win ratio in [Section 7.3.3](#))
- New onset of atrial fibrillation
- Adjudicated MI (fatal or non-fatal)
- Adjudicated stroke (fatal or non-fatal)
- Adjudicated TIA
- Composite of time to first event of all-cause mortality and all cause hospitalisation
- Composite of adjudicated CV death or adjudicated non-fatal MI
- Composite of adjudicated CV death or adjudicated non-fatal stroke
- Adjudicated CV death, adjudicated non-fatal MI, adjudicated non-fatal stroke (3-point MACE)
- Progression to macro albuminuria (defined as UACR >300 mg/g) from baseline for patients with baseline UACR ≤ 300 mg/g
- Time to first new onset of sustained normo- or micro albuminuria (UACR ≤ 300 mg/g) in patients with macro albuminuria at baseline
- Time to first new onset of sustained normo albuminuria (UACR < 30 mg/g) in patients with micro- or macro albuminuria at baseline
- eGFR (CKD-EPI)_{cr} change from baseline to 30 days after treatment stop
- Composite of sustained reduction of ≥40% eGFR (CKD-EPI)_{cr} or sustained eGFR (CKD-EPI)_{cr} <15 mL/min/1.73 m² (< 10 mL/min/1.73 m² for patients with eGFR (CKD-EPI)_{cr} < 30mL/min/1.73 m² at baseline), or adjudicated CV death
- Composite of sustained reduction of ≥40% eGFR (CKD-EPI)_{cr} or sustained eGFR (CKD-EPI)_{cr} <15 mL/min/1.73 m² (< 10 mL/min/1.73 m² for patients with eGFR (CKD-EPI)_{cr} < 30mL/min/1.73 m² at baseline), or all-cause mortality
- Composite of sustained reduction of ≥40% eGFR (CKD-EPI)_{cr} or sustained eGFR (CKD-EPI)_{cr} <15 mL/min/1.73 m² (< 10 mL/min/1.73 m² for patients with eGFR (CKD-EPI)_{cr} < 30mL/min/1.73 m² at baseline), adjudicated CV death, or adjudicated HHF

Proprietary confidential information © 2019 Boehringer Ingelheim International GmbH or one or more of its affiliated companies

- Change from baseline in KCCQ overall summary score at week 52
- Change from baseline in KCCQ total symptom score at week 52
- Change from baseline in KCCQ individual domains at week 52
- Change from baseline in KCCQ based on patient-preferred outcome at week 52
- Change in NYHA class from baseline at week 52
- Change from baseline in Health-related quality of life measured by EQ-5D
- Health economic analysis by Health Care Resource Utilisation
- Changes in NT-proBNP from baseline over time
- Change in albuminuria from baseline over time
- Change in albuminuria from baseline over time by baseline UACR) categories (<30 mg/g, ≥30mg/g to ≤300mg/g, >300 mg/g)
- Incidence of acute renal failure (based on narrow SMQ)
- Time to first acute kidney injury (based on the preferred term)
- Change from baseline in body weight over time
- Change from baseline in Systolic Blood Pressure (SBP) over time
- Change from baseline in Diastolic Blood Pressure (DBP) over time
- Change from baseline in pulse rate over time
- Change from baseline in HbA1c over time in the overall population and in 3 subgroups (non-DM, pre-DM, and DM)

Refer to the trial statistical analysis plan (TSAP) for the complete set of further endpoints.

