7.5 HANDLING OF MISSING DATA

There will be no imputation of data for safety data or for time-to event endpoints. For patients who discontinue the trial treatment prematurely, all efforts will be made to follow patients for survival and for any other endpoints including the primary and key secondary endpoints until the end of the trial.

For the slope analysis of eGFR (CKD-EPI)_{cr}, all available on-treatment change from baseline data will be used. Patients without on-treatment data after randomisation will not be included in this analysis.

For the analysis of change from baseline to 30 days after treatment stop, only available data will be used. Only patients with post-treatment data will be used in this analysis.

For other longitudinal endpoints such as KCCQ scores, MMRM methodology will be used. Models will be run on both all observed data and all observed on-treatment data. Details of the imputation rule will be given in the statistical analysis plan.

Proprietary confidential information © 2019 Boehringer Ingelheim International GmbH or one or more of its affiliated companies

An eGFR (CDK-EPI)_{cr} reduction is considered sustained, if it is determined by two or more consecutive post-baseline central laboratory measurements separated by at least 30 days (first to last of the consecutive eGFR values). If there is no additional measurement after the eGFR reduction is observed and the patient dies within 60 days of this measurement without second measurement ≥ 30 days after the first, then the eGFR reduction is also considered sustained.

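### The three renal composites in Section 5.1.3 omit chronic dialysis and renal transplant, which Section 5.1.2 counts, so a kidney failure can be an event in the secondary endpoint and a non-event in the broader composites

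*Protocol*

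**What the plan says.** Section 5.1.2 of the current protocol (revision of 20 Nov 2019) defines the secondary renal endpoint as "Time to first occurrence of chronic dialysis or renal transplant or sustained* reduction of" at least 40% in eGFR, or a sustained eGFR below 15 (below 10 if baseline eGFR is under 30). It defines dialysis without reference to any laboratory value: "Chronic dialysis is defined as dialysis with a frequency of twice per week or more often for at least 90 days". An eGFR reduction is sustained "if it is determined by two or more consecutive post-baseline central laboratory measurements separated by at least 30 days". Section 7.5 repeats that rule and adds one exception, for the case where "the patient dies within 60 days of this measurement without second measurement" at least 30 days after the first.

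Section 5.1.3 lists three renal composites. Each begins with the same kidney component, "Composite of sustained reduction of ≥40% eGFR (CKD-EPI)_{cr} or sustained eGFR (CKD-EPI)_{cr} <15 mL/min/1.73 m²", with the lower threshold for patients whose baseline eGFR is under 30. They differ only in how they end:

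- "m² at baseline), or adjudicated CV death"
- "m² at baseline), or all-cause mortality"
- "m² at baseline), adjudicated CV death, or adjudicated HHF"

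None of the three names dialysis or transplant. Section 7.3.3 analyses further time-to-event endpoints with the same Cox model as the primary analysis.

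**The concern.** The protocol uses two definitions of a kidney event for what Section 1.2.3 presents as one hypothesis. That section says the renal effect will be examined through the eGFR slope and composite renal endpoints, and it points to both 5.1.2 and 5.1.3.

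A reader will take a composite of a renal event or CV death to contain every renal event that the trial counts elsewhere. As written it does not. A patient on chronic dialysis or with a transplant can be an event in the secondary endpoint and be censored event-free in the composite. The events at risk of being lost are the most severe kidney outcomes. The narrower and broader endpoints then cannot be reconciled in a results table, and a difference between their hazard ratios could reflect the change of definition rather than the added deaths or HHF.

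**Working it through.** The plan gives no figure to reproduce, so the check is a comparison of component lists, followed by an illustrative count.

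**1. Components side by side (current protocol)**

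| Endpoint | Dialysis or transplant (D) | Sustained eGFR criteria (R) | Added components |
|---|---|---|---|
| Secondary renal endpoint, S (5.1.2) | yes | yes | none |
| Composite C1 (5.1.3) | no | yes | CV death |
| Composite C2 (5.1.3) | no | yes | all-cause mortality |
| Composite C3 (5.1.3) | no | yes | CV death, HHF |

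So S = D or R, C1 = R or CV death, C2 = R or any death, and C3 = R or CV death or HHF. D belongs to S and to none of the three composites, so S is not contained in any of them. A patient with D but not R is an event in S and a non-event in C1 without CV death, in C2 without death, and in C3 without CV death or HHF. If R is confirmed, or an added component occurs, only after D, the patient does count in the composite, but with a later event time than in S.

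**2. Can D occur without R?** R needs two consecutive qualifying central values at least 30 days apart. Section 7.5 relaxes this for death only, not for dialysis or transplant. Several parts of the protocol allow D without that pair:

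- On-site visits after week 52 are 24 weeks apart (6.2.2), and telephone contacts yield no central sample.
- Patients off trial medication may be followed by telephone only, or at trial end only (3.3.4.1).
- The repeat sample in 5.3.4.1 is triggered by a qualifying central value or by a signal from others, such as a local laboratory. It requires the patient to attend.
- At the entry floor of eGFR 20 (3.3.3), a 40% fall means 20 × 0.6 = 12 or below, and the absolute threshold is below 10. Such a patient has little room between entry and dialysis in which to be sampled twice.

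In addition, as general knowledge and not from the protocol, dialysis lowers creatinine and a transplant restores filtration, so samples taken afterwards may not qualify. The conclusion does not depend on this.

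**3. How the difference arose.** In protocol version 1.0 the kidney components of 5.1.2 and 5.1.3 were both eGFR-only and agreed. Global Amendment 1 (Section 11.1) added dialysis and transplant to the synopsis and to 5.1.2, reasoning that either one indicates a lasting loss of renal function. The current 5.1.3 composites read as they did in version 1.0. The amendment log as available records no change to them and gives no reason for a difference.

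**4. Illustrative size.** From Section 7.7: 4126 patients, 18 months accrual and 20 months further follow-up. With uniform accrual (assumed), mean follow-up is 20 + 18/2 = 29 months, about 2.4 years, ignoring early deaths and drop-out.

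- Patient-years: 4126 × 2.4 ≈ 9,900.
- Assumed rate of dialysis or transplant, 0.1 to 0.5 per 100 patient-years: 9,900 × 0.001 ≈ 10 to 9,900 × 0.005 ≈ 50 patients.
- Assumed share without a confirmed eGFR criterion, 10% to 50%: 10 × 0.10 = 1 to 50 × 0.50 = 25 patients with the event lost or delayed.

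The rate and the share are both assumptions; the protocol supplies neither.

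**5. After the change.** With D added to each composite, every event in S is also an event in C1, C2 and C3, at the same time or earlier.

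**The case against.** The strongest objection is about importance. These are further endpoints, one tier below other secondary endpoints that are themselves outside the confirmatory hierarchy and exploratory (5.1.2, 7.2). The primary endpoint, recurrent HHF, the eGFR slope and the secondary renal endpoint are untouched, and the last of these already reports dialysis and transplant. All of this stands, and it limits the weight of the point.

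Second, many of these patients will meet the eGFR criterion anyway. A 40% fall is reached at 36 from a baseline of 60, and at 24 from a baseline of 40, so a gradual decliner would normally cross it well before dialysis. The repeat-sample rule in 5.3.4.1 means confirmation does not rest on the 24-week visit interval alone. Some of the remaining patients will die or have an HHF and count that way. This also stands. The gap is mainly abrupt kidney failure and patients without central sampling, so events can be missed, not always are.

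Third, Section 5.1.3 refers to the TSAP for the complete set of further endpoints, and the TSAP may have aligned the definitions. That is possible, and it means one cannot say that the analysed composites lack these events. It does not repair the protocol, where these three composites are already defined and differ from 5.1.2.

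Fourth, the count of 1 to 25 spans a 25-fold range and rests on assumed inputs. That is fair. It illustrates scale and is not evidence; the inconsistency stands without it.

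Finally, the protocol nowhere states that the 5.1.3 composites must contain the secondary endpoint. But it gives no reason for a different kidney component, and the sponsor's rationale for the change to 5.1.2 applies equally to 5.1.3.

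**Conclusion.** The point holds. Sections 5.1.2 and 5.1.3 define the kidney component differently, most plausibly because Amendment 1 was not carried through to 5.1.3. The secondary renal endpoint is therefore not nested in any of the three composites built around the same eGFR criteria. This follows from the text alone and needs no assumption.

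The numerical effect cannot be derived from the protocol. The range of about 1 to 25 patients lost or delayed per composite depends on the assumed event rate, the assumed share without eGFR confirmation and the planned 4126 patients; it would scale with patient-years if enrolment or follow-up were extended. Alpha, power and the confirmatory conclusions are not affected. What is affected is whether the exploratory renal composites capture the most severe kidney outcomes and can be compared with the secondary renal endpoint.

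**What to change.** In Section 5.1.3, add chronic dialysis or renal transplant as the first component of all three renal composites and refer to the definition of chronic dialysis in Section 5.1.2. Check that the TSAP carries the same kidney component. If the difference is intended, state the reason in 5.1.3.

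The cost is a change of wording. Dialysis and transplant data are already needed for the secondary endpoint, so no new data, visits or patients are required, and sample size and alpha are unchanged.

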5.2 ASSESSMENT OF EFFICACY

The CEC is responsible for the adjudication of all relevant CV events, which could potentially fulfil the criteria for the primary, secondary and further endpoints. The CEC charter is available in the ISF for details regarding adjudication. Please also refer to [Section 3.1.1.1](#) for information on the CEC.

5.2.1 KCCQ

KCCQ is a 23-item self-administered questionnaire designed to evaluate physical limitations, symptoms (frequency, severity, and changes over time), social limitations, self-efficacy, and quality of life in patients with HF.

Proprietary confidential information © 2019 Boehringer Ingelheim International GmbH or one or more of its affiliated companies

The paper-and-pen version in the required native language of the patient will be used. If the required language is not available then the patient is not required to complete the questionnaire.

The questionnaire takes about 5-8 minutes to complete and will be distributed according to the [Flow Chart](#).

The Investigator (or designated site-personnel) should ensure that the patient has access to a quiet area at the site where he/she can be left alone to record her/his response in the questionnaire. In instances where a patient cannot give or decide upon a response, no response should be recorded. The Investigator (or designated site-personnel) should check that all items have been completed by the patient, but the response to each item should not be scrutinised. Instructions to patients are included in the questionnaire. The respective procedure for illiterate patients (if included) is described in the [Appendix 10.1](#).

To assess the further endpoint of change from baseline in KCCQ based on patient-preferred outcome at week 52, the investigator or designee will be required to ask the patient one additional question about which domain is the most difficult for the patient to cope with. The response to this question will be recorded in the eCRF.

5.2.2 New York Heart Association classification

The New York Heart Association (NYHA) functional classification will be used to classify the severity of the patients' heart failure (ref. [Appendix 10.3](#)). The investigator should place the patients in one of the four categories based on how limited their physical activity are. Candidates for screening are required to have a NYHA functional class II, III or IV. The classification of patient's physical activity according to NYHA will be performed at all on-site until end of the trial. If a visit is designated as an on-site visit but is conducted by phone, the NYHA functional classification must be performed.

5.2.3 NT-proBNP

Refer to [Section 5.5](#) Assessment of biomarkers

5.2.4 Body weight

BMI (kg/m²) will be calculated for determination of eligibility at Visit 1. Body weight will be measured at all on-site visits:

- after the urine sampling (weight after bladder voiding),
- shoes and coat/jackets should be taken off, and
- pockets should be emptied of heavy objects (i.e. keys, coins etc.).

5.2.5 Blood pressure

SBP and DBP as well as pulse rate (electronically or by palpation, count for 1 minute) will be measured after 5 minutes of rest in the seated position according to the [Flow Chart](#). At visit 1, after the patient has rested quietly, in the seated position for five minutes, three blood pressure measurements will be taken and recorded in the eCRF. The mean of these 3 blood pressure values will be used to determine eligibility. At subsequent visits, blood pressure

Proprietary confidential information © 2019 Boehringer Ingelheim International GmbH or one or more of its affiliated companies

recordings should be measured using a similar type of and validated certified blood pressure recording instrument on the same arm, when possible.

5.3 ASSESSMENT OF SAFETY

5.3.1 Physical examination

A complete physical examination will be performed by the Investigator according to the [Flow Chart](#). Documentation of, and findings from the physical examination, must be part of the source documents available at the site.

5.3.2 Clinical routine examination

During the course of the trial the patient may undergo examinations that are not trial specific but a part of the clinical routine such as:

- ECG
- Echocardiography, radionuclide ventriculography, invasive angiography, MRI or CT.

In order to capture arrhythmias and significant changes in ECG, and LVEF measurements in echocardiography (or similar), the Investigator will be asked to enter the results from these examinations in the eCRF.

If the patient has an ICD the Investigator will be asked to enter information gathered from interrogations of the ICD in the eCRF.

5.3.3 Vital signs

Vital signs to be measured are SBP, DBP and pulse rate.

5.3.4 Safety laboratory parameters

All safety laboratory samples will be collected as described in the [Flow Chart](#).

All parameters that will be determined during the trial conduct are listed in [Table 5.3.4: 1](#). The analysis will be performed by a central laboratory. The respective reference range and details about sample handling and shipment will be provided in the ISF (Lab Manual).

Table 5.3.4: 1 Safety laboratory parameters – whole blood, serum or plasma

Haematology

- Hematocrit
- Haemoglobin
 - Reticulocyte Count (reflex test if Hb outside normal range)
- Red Blood Cells (RBC) / Erythrocytes
- White Blood Cells / Leukocytes
- Platelet Count / Thrombocytes
- Differential Automatic (relative and absolute count):
Neutrophils, Eosinophils, Basophils, Monocytes, Lymphocytes

Clinical chemistry

- Albumin
- Alkaline phosphatase
 - γ -GT (gamma-glutamyl transferase)
reflex test triggered by elevated alkaline phosphatase on two sequential measures
- ALT (alanine transaminase, SGPT)
- AST (aspartate transaminase, SGOT)
- Bicarbonate
- Bilirubin total, fractionated if increased
- Calcium
- Chloride
- Creatinine
- Creatine kinase (CK)
- Hs Troponin I (reflex tests if CK is elevated)
- Glucose
- Magnesium
- Phosphate
- Potassium
- Protein total
- Sodium
- Urea (BUN)
- Uric acid

Lipids

- Cholesterol (total)
- HDL cholesterol
- Calculated LDL cholesterol
- Triglycerides (reflex test for direct measurement of LDL cholesterol triggered if triglycerides are > 400 mg/dl or 4.52 mmol/l)

5.3.4.1 Renal function

Urine albumin/creatinine ratio (UACR) in spot urine will be determined and calculated at the central laboratory.

The estimated glomerular filtration rate (eGFR) will be derived from serum creatinine values, age, sex and race based on the CKD-EPI equation [[R12-1392](#)]:

$$\text{GFR} = 141 \times \min(\text{Scr} / \kappa, 1)^\alpha \times \max(\text{Scr} / \kappa, 1)^{-1.209} \times 0.993^{\text{Age}} \times 1.018 \text{ [if female]} \times 1.159 \text{ [if black]}$$

where:

Scr is serum creatinine in mg/dL,

κ is 0.7 for females and 0.9 for males,

α is -0.329 for females and -0.411 for males,

min indicates the minimum of Scr / κ or 1, and

max indicates the maximum of Scr / κ or 1.

Proprietary confidential information © 2019 Boehringer Ingelheim International GmbH or one or more of its affiliated companies

The race of the patient will be entered because of potential differences due to race. The CKD-EPI equation considers the race as an adjustment factor, therefore the race must be known for accurate estimation.

In case of an eGFR loss of $\geq 40\%$ since baseline, or when the eGFR drops to < 15 mL/min/1.73 m² for patients with an eGFR ≥ 30 mL/min/1.73 m² at baseline (< 10 mL/min/1.73 m² for patients with an eGFR < 30 mL/min/1.73 m² at baseline); an additional visit between 30 days to preferably 60 days after detection should be scheduled (unless detected at the EOT visit at trial end) to collect a blood sample for repeat central analysis of creatinine for calculation of the eGFR. If a signal of abnormal creatinine or eGFR is reported to the site by others (e.g. treating physicians from local labs), an additional sample should be sent to central lab, and if it is still abnormal, another sample should be sent to central lab between 30 days and preferably 60 days.

Kidney function will be classified as described in the table below ([Table 5.3.4.1:1](#)):

Table 5.3.4.1: 1 Classification of kidney function

CKD stage	eGFR
1	≥ 90
2	60-89
3a	45-59
3b	30-44
4	15-29
5	< 15

